3.3. Strata and Covariates

An Interactive Web Response System (IWRS) will be used for centralized randomization and treatment assignment. Randomization will be stratified by

- Presence or absence of diabetes mellitus (as determined by medical history or based on Screening laboratory values if previously undiagnosed [i.e. HbA1c \geq 6.5% or fasting plasma glucose \geq 126 mg/dL])
- ELF score \geq 9.76 or $<$ 9.76 during Screening.

If there are discrepancies in stratification factor values between the IWRS and the clinical database, the baseline values recorded in the clinical database will be used for analyses.

Efficacy endpoints will be evaluated using stratification factors as covariates for analyses, as specified in Section 6.

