### Biomarker Tests:

Including but are not limited to C-reactive protein (CRP), ELF™, and FibroSURE/FibroTest®.

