## **8.6. Efficacy Analysis**

### **8.6.1. Primary Efficacy Endpoints Analysis**

#### **Primary Histology Efficacy Endpoint Analysis**

A stratified MH test will be used to compare the differences in proportions of subjects who achieve a  $\geq 1$ -stage improvement in fibrosis without worsening of NASH at Week 48 between each of the SEL arms and the placebo arm, adjusting for stratification factors. Subjects with missing data regarding fibrosis stage and NAS elements used to define worsening of NASH (hepatocellular ballooning and lobular inflammation) at Week 48 will be analyzed as treatment failures. The point estimates and 95% confidence intervals for the differences in proportions will be calculated.

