1.2. Study Design

This is a Phase 3, randomized, double-blind, placebo-controlled study evaluating the safety and efficacy of SEL in subjects with NASH and bridging (F3) fibrosis.

The overall study design is presented graphically in [Figure 1-1](#).

Figure 1-1. Overall Study Design

- EOT = end of treatment; ET = early termination; PTM = Placebo-to-Match

Subjects meeting the study’s entry criteria were randomly assigned in a 2:2:1 ratio to 1 of 3 treatment groups: Group A, Group B and Group C, respectively, as shown in [Figure 1-1](#). Randomization was stratified by the presence or absence of diabetes mellitus (determined by medical history or based on Screening laboratory values if previously undiagnosed [ie, hemoglobin A1c (HbA1c) \geq 6.5% or fasting plasma glucose \geq 126 mg/dL]) and by Enhanced Liver Fibrosis (ELF™) test score \geq 9.76 or $<$ 9.76 during Screening. Study drugs will be administered for up to a total of 240 weeks.

Subjects who experience a clinical event (except all-cause mortality and liver transplantation) prior to completing the Week 240 Visit of the Randomized Phase will be offered the option to rollover into an Open-Label (OL) Phase for a total treatment duration of 240 weeks inclusive of the Randomized Phase. Rollover into the OL Phase of the study must occur within 60 days of confirmation of the event. Subjects starting the OL Phase of the study will complete the same study procedures as during the Randomized Phase of the study, **CCI**

The schedule of assessments is provided as an appendix to this analysis plan ([Appendix 1](#)).

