3.8.3. Selection of Data in the Event of Multiple Records in an Analysis Visit Window

Depending on the statistical analysis method, single values may be required for each analysis window. For example, change from baseline by visit usually requires a single value, whereas a time-to-event analysis would not require 1 value per analysis window.

If multiple, valid, nonmissing, continuous measurements exist in an analysis window, records will be chosen based on the following rules if a single value is needed:

- In general, the baseline value will be the last nonmissing value on or prior to the first dosing date of study drug in the corresponding phase. If multiple measurements occur on the same day, the last nonmissing value prior to the time of first dosing of study drug will be considered as the baseline value. If these multiple measurements occur at the same time or the time is not available, the average of these measurements (for continuous data) will be considered as the baseline value. Baseline values for liver tests (ALT, AST, total bilirubin and direct bilirubin) in the Randomized Phase will be determined by averaging the values obtained between and including Screening and Day 1; baseline values for liver tests (ALT, AST, total bilirubin, and direct bilirubin) in the OL Phase will be determined by averaging the values obtained between OL Study Day - 55 and OL Study Day 1 (inclusive); baseline values for elastography will be determined as the last nonmissing values on or prior to (OL) Day 28. Missing (OL) Baseline/Day 1 values of HRQoL questionnaires and HRUQ will not be imputed.
- For postbaseline visits:
 - 1) The record closest to the nominal day for that visit will be selected.
 - 2) If there are 2 records that are equidistant from the nominal day, the later record will be selected.
 - 3) In general, if there is more than 1 record on the selected day, the average will be taken. For serum creatinine, if both enzymatic and regular creatinine are collected from the same blood sample and are analyzable, regular creatinine will be selected for analysis.

If multiple, valid, nonmissing, categorical measurements exist in an analysis window, records will be chosen based on the following rules if a single value is needed:

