6.1.3. Analysis of Primary Histology Efficacy Endpoint

A stratified Mantel-Haenszel (MH) test will be used to compare the differences in proportions of subjects who achieve a ≥ 1 -stage improvement in fibrosis without worsening of NASH at Week 48 between SEL 18 mg (SEL 6 mg) and placebo, adjusting for the presence or absence of diabetes mellitus at baseline and ELF test score ≥ 9.76 or < 9.76 at baseline. Subjects with missing data regarding fibrosis stage and NAS elements used to define worsening of NASH (hepatocellular ballooning and lobular inflammation) at Week 48 will be analyzed as treatment failures for this endpoint. The 2-sided 95% CIs for the difference in proportions between SEL 18 mg (SEL 6 mg) and placebo will be constructed based on stratum-adjusted MH proportions as follows {Koch 1989}:

$$p_A - p_B \pm Z_{(1-\alpha/2)} * SE(p_A - p_B),$$

where

- $(p_A - p_B) = \frac{\sum w_h d_h}{\sum w_h}$, is the stratum-adjusted MH proportion difference, where $d_h = p_{Ah} - p_{Bh}$ is the difference in the proportion of subjects who achieved a ≥ 1 -stage improvement in fibrosis without worsening of NASH between SEL 18 mg (SEL 6 mg) and placebo in stratum h.

- $w_h = \frac{n_{Ah}n_{Bh}}{n_{Ah} + n_{Bh}}$, is the weight based on the harmonic mean of sample size per treatment group for each stratum where n_{Ah} and n_{Bh} are the sample sizes of SEL 18 mg (SEL 6 mg) and placebo in stratum h.

- $SE(p_A - p_B) = \sqrt{\frac{\sum w_h^2 \left[\frac{p_{Ah}^*(1-p_{Ah}^*)}{n_{Ah}-1} + \frac{p_{Bh}^*(1-p_{Bh}^*)}{n_{Bh}-1} \right]}{(\sum w_h)^2}}$, where

$$p_{Ah}^* = \frac{m_{Ah} + 0.5}{n_{Ah} + 1} \text{ and } p_{Bh}^* = \frac{m_{Bh} + 0.5}{n_{Bh} + 1}, \text{ and}$$

m_{Ah} and m_{Bh} are the number of subjects who achieved a ≥ 1 -stage improvement in fibrosis without worsening of NASH in SEL 18 mg (SEL 6 mg) and placebo in stratum h.

- $\alpha = 0.05$ for the calculation of 95% CI
- $Z_{(1-\alpha/2)} = Z_{0.975} = 1.96$ is the 97.5th percentile of the normal distribution
- $Z \text{ score} = \frac{(p_A - p_B)}{SE(p_A - p_B)}$

If the computed lower confidence bound is less than -1 , the lower bound is defined as -1 . If the computed upper confidence bound is greater than 1 , then the upper bound is defined as 1 .

The point estimates, 95% CIs, and corresponding p-values based on Z tests for the differences in proportions, and the 95% CIs for proportion of responders in each treatment group based on the Clopper-Pearson method will be calculated.

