6.2.3. Analysis of Clinical Efficacy Endpoint

Differences in EFS between SEL 18 mg (SEL 6 mg) and placebo will be assessed using the log-rank test stratified by presence or absence of diabetes mellitus and ELF test score ≥ 9.76 or < 9.76 at baseline.

Time (in months) to the first clinical event/censoring date will be calculated as: $[\text{first clinical event date or censoring date} - \text{randomization date} + 1] / 30.4375$.

Censoring date will be the later date between the last visit date and latest AE onset date in the Randomized Phase for subjects who have prematurely discontinued from the Randomized Phase, or who have completed the Randomized Phase. For the Week 48 Interim Analysis, the data cut date will be used as the censoring date for ongoing subjects in the Randomized Phase.

For the purpose of analysis, if the onset date of a clinical event or an AE is incomplete, the first day of the month (if date is missing) or the first day of the year (if date and month are missing) will be used to derive the clinical event or censoring date. If such imputation leads to an imputed event date that is earlier than the randomization date, then the randomization date should be used to impute the incomplete event date.

In the following code, *Months* is the number of months from randomization date to the first clinical event or to the censoring date for subjects who don't have clinical events. *Status* is a binary variable with 1 representing no clinical event observed and 0 representing a clinical event observed.

```
proc lifetest data=efs_2groups;  
    time Months*Status(1);  
    strata BL_Diabetes BL_ELF_category / group=treatment;  
run;
```

A proportional hazards model will be used to calculate the point estimate and 95% CIs for the hazard ratio between SEL 18 mg (SEL 6 mg) and placebo controlling for stratification factors. Proportional hazard assumption will be evaluated.

```
proc phreg data=efs_3groups;  
    class treatment BL_Diabetes BL_ELF_category;  
    model Months*Status(1) = treatment / RL;  
    strata BL_Diabetes BL_ELF_category;  
run;
```

For each treatment group, the KM estimates of EFS probability at 3-month intervals (ie, at Month 3, 6, 9, etc) and 95% CIs will be provided. The 95% CI will be calculated based on Greenwood's formula and log-log transformation of the survival function.

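### Does stratifying the analyses by baseline ELF, when randomization used Screening ELF, weaken the Week 48 and EFS tests?

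*SAP*

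**What the plan says.** SAP section 1.2 describes randomization as stratified by diabetes "and by Enhanced Liver Fibrosis (ELF™) test score", cut at 9.76 and measured during Screening. SAP section 3.3 repeats this. It then adds that, if the stratification factors differ between the IWRS and the clinical database, "the baseline values recorded in the clinical database will be used for analyses".

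The primary test in SAP section 6.1.3 is a stratified Mantel-Haenszel comparison "adjusting for the presence or absence of diabetes mellitus at baseline and ELF test score ≥ 9.76 or < 9.76 at baseline". The EFS log-rank code in SAP section 6.2.3 reads "strata BL_Diabetes BL_ELF_category / group=treatment". The protocol's description of the primary analysis (section 8.6.1) says only "adjusting for stratification factors".

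Three further provisions bear on the meaning of baseline ELF:

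- SAP section 3.8.3 sets the general rule that "the baseline value will be the last nonmissing value on or prior to the first dosing date of study drug". Table 3-3 gives the ELF baseline window no lower limit and an upper limit of day 1.
- Protocol section 6.11.1 describes the biomarker tests as "Including but are not limited to C-reactive protein (CRP), ELF™, and FibroSURE/FibroTest". The study procedures table schedules biomarker blood at both Screening and Day 1.
- SAP section 4.1, on enrollment by stratum, speaks of disagreement between the IWRS and the database in the value that was used to assign the stratum.

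**The concern.** Read in sequence, these provisions suggest a mismatch. The stratum at randomization comes from the Screening ELF. The general baseline rule selects the last value up to first dose, which is the Day 1 ELF whenever it exists, drawn up to 8 weeks later. SAP section 3.8.3 makes exceptions for liver tests and elastography but none for ELF. On that reading, section 3.3 does more than correct IWRS entry errors: any subject whose two readings fall on opposite sides of 9.76 moves to another stratum.

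The usual principle is that the analysis reflects the randomization. The same strata definition serves the Week 48 test, which decides whether EFS is tested and whether the trial continues, and the EFS test itself. If the strata were wrong in a way that mattered, type I error, power or the estimate could suffer on both endpoints. The change would also be missing from the list of departures from the protocol in SAP section 6.5.

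**Working it through.** **Which ELF value forms the strata.** No sentence in either document says that it is the Day 1 draw. Section 3.3 is conditional on a discrepancy in the stratification factor, and it defines that factor as ELF during Screening. A different Day 1 reading is not a discrepancy in a Screening value. Section 4.1 fits this, as does protocol section 8.5, which compares the IWRS group with the group derived from the database. SAP section 6.3.2 treats baseline ELF category as identical to a stratification factor. The Day 1 reading requires the general baseline rule, Table 3-3 and the visit schedule to be combined. Both readings are possible, so the rest of the check takes the less favourable one.

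**How many subjects could change stratum.** The documents give no ELF mean, variability or discordance rate, so this rests on assumptions.

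- With the cut at the median and two bivariate normal readings with correlation rho, the share that changes is arccos(rho)/pi. This gives 20% at rho 0.80, 14% at 0.90 and 10% at 0.95.
- With mean ELF 9.4 to 10.1, between-subject SD 0.7 to 1.1 and within-subject SD per reading 0.1 to 0.4, the share is 3.9% to 22.8%, or about 31 to 183 of 800 subjects.

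**The plan's own power figures.** Inputs from SAP section 1.3 are 320 versus 160 subjects, 27% versus 12% response, and two-sided alpha 0.025 (z = 2.241).

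- Pooled proportion: (160 × 0.12 + 320 × 0.27)/480 = 0.22.
- Null SE: sqrt(0.22 × 0.78 × (1/160 + 1/320)) = 0.0401.
- Alternative SE: sqrt(0.12 × 0.88/160 + 0.27 × 0.73/320) = 0.0357.
- Power: Phi((0.15 − 2.241 × 0.0401)/0.0357) = 95.4%. With the continuity correction 0.5 × (1/160 + 1/320) = 0.0047 it is 94.0%, the stated figure.
- For EFS, 160 × 0.30 + 320 × 0.163 = 100 events and HR 0.50 give 84.8% by Schoenfeld's formula before any dropout loss, against the stated 85%.

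Neither calculation uses the strata, so neither changes with the choice of ELF value.

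**Validity.** The Day 1 assessments are made before dosing (protocol section 6.3.1) and the trial is double-blind, so treatment cannot influence the Day 1 ELF. Allocation is 2:1 within every Screening stratum, and hence in expectation within every Day 1 stratum. A comparison stratified on any pre-treatment covariate is then a valid test without bias. The Screening reading carries measurement error too, so neither reading is the error-free one.

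**Type I error and power.** The SAP 6.1.3 Z-test was simulated with permuted 2:1 blocks within the Screening strata. Assumptions: mean ELF 9.76, between-subject SD 0.9, 70% diabetic, and placebo response 6% at or above the cut and 18% below it (average 12%). There were 12,000 trials under the null and 6,000 at the 15-point effect.

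| Within-subject SD | Change stratum | Type I error, Screening / Day 1 strata | Power, Screening / Day 1 strata |
|---|---|---|---|
| 0.1 | 5% | 2.36% / 2.35% | 96.4% / 96.4% |
| 0.3 | 14% | 2.21% / 2.13% | 97.2% / 97.2% |
| 0.4 | 19% | 2.14% / 2.15% | 96.9% / 96.8% |

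The simulation error of one type I estimate is about sqrt(0.025 × 0.975/12,000) = 0.14 points, larger than any difference between the paired columns. Further runs at 10% to 20% mismatch gave 2.0% type I error under both stratifications and power within 0.2 points, or 0.3 when ELF was made very strongly prognostic.

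**How often the decision differs.** At 10% to 20% mismatch, the two stratifications disagree on significance in 0.4% to 0.8% of trials at the planned effect and in 0.2% to 0.5% under the null. When the true effect is small enough that power is about 83% to 87%, they disagree in 1.5% to 3%. The disagreements have no direction.

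**The case for a change.** The best case against the plan is that a confirmatory covariate should have one definition. Section 3.3 refers to baseline values and section 4.1 to the value used for assignment, and the general baseline rule, taken literally, leads to Day 1. The protocol calls for adjustment by the stratification factors and says that discrepancies will be listed; it does not say they will replace the strata. The Week 48 test is a gate, and a borderline result could turn on which draw is used. The visible text plans no analysis with the as-randomized strata, and adding one would cost almost nothing.

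Part of this stands: the SAP could have said outright which ELF value defines the baseline category. The rest does not amount to a flaw. The protocol names no data source for the strata and leaves details to the SAP (section 8.1), so section 6.5 has no departure to list. The SAP is to be finalized before the Week 48 unblinding. Occasional disagreement on borderline results arises between any two valid covariate definitions and shows neither to be wrong. Moving to IWRS strata while keeping database values for subgroups would also disturb section 6.3.2, which drops a factor from the adjustment only when the subgroup variable is identical to it.

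**Conclusion.** The concern does not hold. On the natural reading of SAP sections 3.3 and 4.1, the database value is the corrected copy of the Screening ELF, and nothing departs from the randomization except entry errors. On the other reading, an unknown share of subjects (3.9% to 22.8% under the assumptions above) would be analysed in a different ELF stratum. The test would still be valid, type I error would stay at or below 2.4% against a nominal 2.5%, and power would move by at most 0.3 points. Using IWRS strata instead would improve no stated figure and remove no bias; reasonable statisticians choose either.

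The sizes rest on assumed ELF variability, diabetes share and prognostic strength, since the documents give none of these. The EFS log-rank test was not simulated; for it the conclusion rests on the same argument, that the covariate is measured before treatment. The exact definition of the baseline ELF category is a missing detail, and the results are sound whichever way it is settled.

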3.4. Examination of Subject Subgroups

The primary and key secondary efficacy endpoints as defined in Section 6 will be examined using the following subgroups:

- Subjects with diabetes at baseline
- Subjects without diabetes at baseline
- Subjects with ELF test score ≥ 9.76 at baseline
- Subjects with ELF test score < 9.76 at baseline
- Subjects with body weight loss $\geq 5\%$ at Week 48/Week 240 (for Week 48/240 analysis, respectively)
- Subjects with body weight loss $< 5\%$ or body weight gain at Week 48/Week 240 (for Week 48/240 analysis, respectively)
- Subjects treated with Vitamin E at baseline
- Subjects not treated with Vitamin E at baseline
- Subjects with a history of sustained virologic response (SVR) to therapy for chronic hepatitis C virus (HCV)
- Subjects without a history of SVR to therapy for chronic HCV.

For the comparison of the treatment differences in each subgroup, point estimate and 95% confidence intervals (CIs) based on the primary analysis approach will be presented.

3.5. Multiple Testing

[figure not shown]
When the primary histology efficacy endpoint is compared between each of the SEL arms and the placebo arm at Week 48, it will be tested at a 2-sided 0.025 significance level to control for an overall Type I error rate of 0.05 by Bonferroni adjustment.

The testing strategy for the clinical efficacy endpoint (EFS) is described below and is presented graphically in [Figure 3-1](#).

- 1) If the primary histology efficacy endpoint is significant in both SEL arms, the EFS endpoint will be tested for both SEL arms against placebo at Week 240 at a 2-sided 0.05 significance level by the Hochberg procedure {[Hochberg 1988](#)}. If the larger p-value of SEL18 mg versus placebo and SEL 6 mg versus placebo is less than or equal to 0.05, the EFS endpoint for both SEL arms will be a success; if the larger p-value is > 0.05 , the treatment arm with the larger p-value fails, and the smaller p-value will be compared with the significance level of 0.025 to determine the success of the treatment arm.

- 2) If the primary histology efficacy endpoint is significant in the SEL 18 mg arm but not the SEL 6 mg arm, the EFS endpoint will be tested for SEL 18 mg against placebo at Week 240 at a 2-sided 0.025 significance level.
- 3) If the primary histology efficacy endpoint is significant in the SEL 6 mg arm but not the SEL 18 mg arm, the EFS endpoint will be tested for SEL 6 mg against placebo at Week 240 at a 2-sided 0.025 significance level.
- 4) If the primary histology efficacy endpoint is not significant in either the SEL 18 mg or SEL 6 mg arms, the trial will be terminated.

Figure 3-1. Multiple Testing Flow Chart

* Nominal alpha will be adjusted using the Haybittle-Peto approach

Although no formal statistical inference on EFS is planned for the Week 48 Interim Analysis, the actual nominal significance level for the EFS endpoint at the Week 240 Analysis will be adjusted using the Haybittle-Peto approach {[Haybittle 1971](#)}. The adjustment will be based on the number of events at both the Week 48 and Week 240 analyses, assuming an allocation of a 2-sided significance level of 0.001 at the Week 48 Interim Analysis.

3.6. Missing Data and Outliers

3.6.1. Missing Data

For missing last dosing date of study drug, imputation rules are described in Section 4.2.1. The handling of missing or incomplete dates for AE onset is described in Section 7.1.5.3, and for prior and concomitant medications in Section 7.4.

The following imputation approaches will be applied to efficacy endpoints as specified:

1) Non-Responder Imputation (NRI)

For purpose of analysis at a defined time point, when NRI is used, all subjects with missing values will be analyzed as not meeting the corresponding endpoint. The NRI method will be applied to subjects with or without baseline value.

2) Multiple Imputation (MI):

The MI procedure replaces each missing data point of the binary primary histology efficacy endpoint (defined in Section 6.1.1) with a set of plausible values that represent the uncertainty about the right value to impute under the missing at random (MAR) assumption. The imputation model used to impute missing data points will be based on the logistic regression with the treatment arms and the 2 stratification factors as covariates. A total of 50 imputed datasets will be generated by the imputation model. That is, each missing data point will be imputed 50 times. Each imputed data set will be analyzed by the method for the primary analysis as specified in Section 6.1.3. The results from these 50 imputed data sets will be combined using Rubin's rule {[Rubin 1987](#)}.

3) Tipping Point Analysis (TPA):

If any significant result in favor of SEL 18 mg or SEL 6 mg is detected in the primary analysis of the binary primary histology efficacy endpoint (described in Section 6.1.3), a delta-adjusting pattern-mixture approach for TPA {[Ratitch 2013](#)} will be conducted to assess the robustness of the primary analysis results under a missing not at random assumption for SEL arms. Specifically, it is assumed that a systematic difference exists between the conditional distributions of the missing and observed data in the SEL arms. To reflect such a systematic difference, a shift parameter δ will be applied to the imputation model (ie, the logistic regression with the treatment arms and the 2 stratifications factors as covariates) when the missing data points in the SEL arms are imputed. For each value of δ , multiply imputed data sets will be generated, each data set will be analyzed by the same method for the primary analysis, and analysis results will then be combined by Rubin's rule. Thus, by

varying the values of δ , the impact from missing data on the analysis results will be examined to identify tipping points (ie, the values at which conclusions from statistical inference change from being significant to being insignificant for SEL arm(s)).

4) Last Observation Carried Forward (LOCF)

For purpose of analysis at a defined time point, if the value is missing, the last observed value prior to the time point will be used to impute the missing value. Refer to Section 3.8.2 for the handling of the data to be included in efficacy analysis. The LOCF approach will be applied to those subjects who have a baseline value. No imputation will be performed if the value at baseline is missing.

5) Observed Case (OC)

Only subjects with observed Baseline and Week 48/240 values will be included at the corresponding Week 48/240 analysis.

6) Kaplan-Meier Multiple Imputation (KMMI)

Sensitivity analysis will be performed under the KMMI strategy {Zhao 2014} if there are significant differences in the Kaplan-Meier (KM) estimates of survival rates between SEL 18 mg or SEL 6 mg and placebo. This method introduces a sensitivity parameter, θ , defined as the fixed hazard ratio of a subject who dropped out having the event after being censored at a certain centering time relative to subjects who remain on treatment having the event after that censoring time. The MAR-like assumption (ie, noninformative independent censoring) corresponds to $\theta = 1$. $\theta > 1$ implies a higher hazard after censoring for subjects who drop out compared with their counterparts who remain on treatment. By varying the values of θ , the KMMI strategy addresses departures from the MAR-like assumption when unobserved time-to-event data are multiply imputed. The KMMI approach can be summarized as follows:

- i). Calculate KM estimates of survival rates for each treatment group within each stratum separately.
- ii). Obtain the survival estimate at each censoring time by linear interpolation of the KM survival rates corresponding to the 2 event times immediately before and after. The KM survival function may be extrapolated to calculate the survival estimates at censoring time which is after the event time of the last observed event up to the maximum follow-up time (ie, 252 weeks [or 58 months]).
- iii). Apply each value of θ to impute the unobserved event time for a dropout subject who will experience the event after the time being censored for a total of 50 times.

After the multiple imputation, the pairwise logrank test will be performed to compare the survival rates between SEL 18 mg or SEL 6 mg and placebo on each complete data set (described in Section 6.2.3). Then, by combining the normalized chi-square statistics using Rubin's rule, the impact of departures from noninformative censoring can be investigated by

the combined treatment effect inference, which is a function of θ . Thus, the robustness of the significant results can be assessed.

The NRI approach will be used for the primary analysis of the primary histology efficacy endpoint and secondary endpoints evaluated at Week 48. LOCF analysis and OC analysis will be carried out as sensitivity analyses for these endpoints at Week 48 using the same analysis method as defined in Section 6.1.3. “Last observation” includes both baseline and postbaseline records, and only the records eligible for efficacy analysis will be carried forward.

The MI and TPA approaches will be used for the sensitivity analyses for the primary histology efficacy endpoint. KMMI approach will be used for the sensitivity analysis for the clinical efficacy endpoint.

The NRI approach will be used for the primary analysis for the secondary endpoints evaluated at Week 240. The LOCF and OC approaches will be used for sensitivity analysis of these endpoints.

CCI

In the subgroup analysis by body weight change from baseline, missing Week 48/Week 240 (for the Week 48/240 analysis, respectively) body weight will be imputed using the LOCF approach to determine which subgroup a subject belongs to.

